At the end of the study, the sponsor should notify the IRB/IEC and Competent Authority within 90 days. The definition for end of the study is the date of data cutoff for the final analysis or last subject/last visit including discontinuation from the study for any reason, whichever occurs later. Subjects who remain on treatment at the cutoff for the final analysis will continue receiving the same treatment in consecutive cycles as long as they do not meet any of the study discontinuation criteria as detailed in the protocol.

In the case of early termination/temporary halt of the study, the investigator should notify the IRB/IEC and Competent Authority within 15 calendar days, and a detailed written explanation of the reasons for the termination/halt should be given.

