9.7 Statistical Methods

All statistical analyses will be performed by the sponsor or designee after the study is completed and the database is locked and released. Statistical analyses will be performed using SAS software or other validated statistical software as required. Details of the statistical analyses will be included in a separate statistical analysis plan (SAP).

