9.7.1.6 Efficacy Analyses

Data cutoff for the primary study analysis in Phase 2 will occur when all evaluable subjects have completed at least 4 treatment cycles and, if applicable, a confirmatory scan has been performed (in case of a PR or CR at Week 16), or have discontinued study treatment early.

The following are evaluability criteria for objective response and non-target disease response analysis:

- **Evaluable for objective response:** Only those subjects who have measurable disease present at baseline and have their disease re-evaluated at post-baseline visits will be considered evaluable for objective response. These subjects will have their response classified according to RECIST 1.1 (for Ewing sarcoma/pPNET and rhabdomyosarcoma) or RANO (for HGG).
- **Evaluable for non-target disease response:** Subjects who have lesions present at baseline that are evaluable but do not meet the definitions of measurable disease and have had their disease re-evaluated at post-baseline visits will be considered evaluable for non-target disease. Subjects with only non-target disease will be summarized by their best overall response. The response will be classified according to RECIST 1.1 defined categories for subjects with non-target disease only.

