5 STATISTICAL METHODS

All descriptive statistics for continuous variables will be reported using n, mean, SD, median, 25th percentile (Q1), 75th percentile (Q3), minimum and maximum. Categorical variables will be summarized as number (percentage) of subjects. The statistical analyses of the study data as described in this section will be performed as further outlined in this SAP, which will be finalized before database lock and included in the CSR.

For Phase 1, data cutoff will occur when the MTD/RP2D for the lenvatinib/everolimus combination is determined, or if the PK expansion is needed, will occur when the last subject in the PK expansion completes 1 cycle of treatment or discontinues before the end of Cycle 1, whichever occurs first. Additional subjects enrolled for PK once the MTD or RP2D has been defined will not be included in the DLT analysis.

For each cohort in Phase 2, there will be 1 futility analysis: this is planned after the first 10 subjects have completed at least 4 treatment cycles and, if applicable, a confirmatory scan has been performed (in case of a PR or CR at week 16), or have discontinued study drug early (i.e. before Week 16). At the futility analysis, if there are no responders (CR/PR), then enrollment for that cohort will be discontinued for lack of efficacy. If 1 or more responses are observed, accrual will continue up to a total of 20 subjects. Data cut-off for the primary study analysis for each cohort in Phase 2 will occur when all subjects in Stage 1 and/or Stage 2, as applicable, have completed at least 4 treatment cycles and, if applicable, a confirmatory scan has been performed (in case of a PR or CR at Week 16), or have discontinued study drug early.

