5.1.2 Secondary Endpoints

Secondary endpoints for Phase 1 and Phase 2 are listed below.

- ORR at the time of data cutoff
- DCR, defined as the proportion of subjects who have the BOR of CR or PR or stable disease (SD) (SD duration ≥ 7 weeks since the first dose of the study treatment)
- CBR, defined as the proportion of subjects who have the BOR of CR or PR or durable SD (SD duration ≥ 23 weeks since the first dose of the study treatment)
- DOR, defined as the time from the date of the first documented CR or PR to the date of the disease progression objectively documented or death (whichever occurs first)
- Plasma PK of lenvatinib and trough concentrations of everolimus when administered in combination
- Safety and toxicity of lenvatinib in combination with everolimus in Phase 2.

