5.2 Study Subjects

5.2.1 Definitions of Analysis Sets

The following analysis sets will be defined:

- **Evaluable Analysis Set**, defined as all evaluable subjects, who have measurable disease present at baseline and at least 1 postbaseline efficacy assessment, unless they have discontinued prior to the first efficacy assessment due to progressive disease. Efficacy analyses in Phase 2 will primarily be based on the Evaluable Analysis Set.
- **Safety Analysis Set**, defined as all subjects who received at least 1 dose of study drug (lenvatinib or everolimus). This will be the analysis set for disposition, demographic and baseline characteristics, previous anticancer medications, prior and concomitant medications, procedures and radiotherapy, medical history, efficacy analysis in Phase 1 as well as all safety evaluations.
- **Pharmacokinetic (PK) Analysis Set**, defined as subjects in the Safety Analysis Set who had at least 1 measurable postdose plasma concentration with an adequately documented drug administration history.
- **Pharmacodynamic Analysis Set**, defined as all subjects in Safety Analysis Set who had evaluable pharmacodynamic data.

All analyses will be presented by planned dose level group in Phase 1 and separately for each study cohort in Phase 2, unless otherwise specified. A summary table and listing will also be provided to identify subjects in each analysis set.

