5.4 Primary, Secondary and Exploratory Analyses

5.4.1 Primary Analyses

5.4.1.1 Dose-Finding Analysis in Phase 1

The primary objective of Phase 1 is to determine the MTD and to establish RP2D of lenvatinib administered in combination with everolimus. The study will utilize the rolling 6 design detailed in SAP [Section 3.2](#).

5.4.1.2 Primary Efficacy Analysis for Phase 2

Efficacy analyses for Phase 2 will be performed separately for each study cohort.

The primary objective of Phase 2 is to estimate the antitumor activity of lenvatinib in combination with everolimus in pediatric subjects with Ewing sarcoma/peripheral primitive neuroectodermal tumor (pPNET), rhabdomyosarcoma, and HGG using the ORR at 16 weeks. The ORR at Week 16 is defined as the proportion of subjects who have the BOR of CR or PR at Week 16.

Subjects must have measurable disease present at baseline for Phase 2. Those who have their disease re-evaluated at postbaseline visits will be considered evaluable for objective response. Estimated ORR and its exact 95% CI using the Clopper-Pearson [Clopper and Pearson, 1934] method will be presented.

The data cutoff for the primary study analysis in Phase 2 will occur when all evaluable subjects have completed at least 4 treatment cycles and, if applicable, a confirmatory scan has been performed (in case of a PR or CR at Week 16), or have discontinued study treatment early.

Tumor response data utilized in the primary analysis of ORR will be obtained from investigator's assessment of the imaging scans. No independent tumor assessments will be performed as part of this study. Tumor response will be assessed by RECIST 1.1 criteria [Eisenhauer, et al., 2009] in pediatric subjects with Ewing sarcoma/peripheral primitive neuroectodermal tumor (pPNET) and rhabdomyosarcoma, and RANO criteria will be used for subjects with HGG [Wen, et al., 2010]. Efficacy analyses in Phase 2 will primarily be based on the Evaluable Analysis Set .

The BOR is determined once all data for a subject is known. For this study, a confirmation of CR or PR is required for both RECIST 1.1 and RANO. The confirmation assessments should be made ≥ 4 weeks after the initial response assessment. The BOR is determined by sequentially checking two adjacent assessments (≥ 4 weeks apart).

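### Phase 1 CBR and DCR keep late-enrolled subjects in the denominator although the SAP's data cutoff leaves them too little follow-up to qualify

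*SAP*

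**What the plan says.** **Phase 1 cutoff.** SAP Section 5 puts it at the determination of the MTD/RP2D. If there is a PK expansion, cutoff "will occur when the last subject in the PK expansion completes 1 cycle of treatment or discontinues before the end of Cycle 1". A cycle is four weeks. The sentence is not limited to any particular endpoint.

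**Endpoints.** SAP 5.1.2 gives "CBR, defined as the proportion of subjects who have the BOR of CR or PR or durable SD", with durable meaning at least 23 weeks from first dose. DCR uses 7 weeks. SAP 5.4.2.1 assigns a best response of stable disease only if it is documented 7 weeks or more after first dose.

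**Scans.** SAP 8.1 schedules Phase 1 scans at Weeks 4, 12 and 24, each within a week either way. Phase 2 scans are at Weeks 8, 16 and 24.

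**Denominators.** SAP 5.2.1 and Appendix 13.1 base Phase 1 efficacy on the Safety Analysis Set, that is, anyone who took a dose. SAP 5.4.2.1 splits it by measurable or evaluable disease. No minimum follow-up applies. The Evaluable Analysis Set, used in Phase 2 (and for all efficacy in Protocol 9.7.1.2), has none either.

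**Phase 2 cutoff.** SAP Section 5 sets it by cohort: "Data cut-off for the primary study analysis for each cohort in Phase 2 will occur when all subjects in Stage 1 and/or Stage 2" have finished four cycles, had a confirmatory scan where one is due, or stopped early. SAP 5.4.1.2 has instead "The data cutoff for the primary study analysis in Phase 2 will occur when all evaluable subjects have completed at least 4 treatment cycles", and Protocol 9.7.1.6 agrees with it: "Data cutoff for the primary study analysis in Phase 2 will occur when all evaluable subjects have completed at least 4 treatment cycles".

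**Rules for incomplete follow-up.** SAP 5.3.5 covers only adverse events and concomitant medications. Table 3 censors only duration of response (DOR).

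**The concern.** CBR and DCR are simple proportions with a time requirement built into the numerator. A subject who entered shortly before cutoff and is still in stable disease has not failed; the outcome is not yet known. The same holds for a response seen at the Week 4 scan and not yet confirmed. Because the denominator has no follow-up condition and no rule sets these subjects aside, they are in effect scored as non-qualifying.

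The error runs one way and depends on enrolment date rather than on the treatment. It falls hardest on any PK-expansion subjects, who enter last and whom SAP Section 4 places at the RP2D. At stake are named secondary endpoints, their exact confidence intervals, and the comparison of dose levels in Phase 1.

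**Working it through.** The plan gives no figure for follow-up at cutoff. Its one design figure, 88% power at one-sided alpha 0.07, reproduces (exact two-stage calculation with 0/10 and 2/20: power 0.882, alpha 0.0686). It does not bear on this point.

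**1. Guaranteed follow-up against threshold**

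| Rate | Guaranteed weeks | Needed weeks | Shortfall |
|---|---|---|---|
| Phase 1 CBR | 4 | 23 | 19 |
| Phase 1 DCR, by definition | 4 | 7 | 3 |
| Phase 1 DCR, by scan schedule | 4 | 11 | 7 |
| Phase 2 CBR, primary-analysis cutoff | 16 | 23 | 7 |
| Phase 2 DCR | 16 | 7 | 0 |

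The 11 arises because the Week 4 scan, even a week late, falls at Week 5. The next scheduled scan is Week 12, at the earliest Week 11. If the last Phase 2 subject needs a confirmatory scan, guaranteed follow-up is about 20 weeks and the CBR shortfall is 3.

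**2. Phase 1 overall** (assumption: uniform accrual)
- Accrual: 18 months (SAP Section 4) is about 78 weeks; 78 − 4 = 74 weeks.
- Under 23 weeks at cutoff: 19/74 = 25.7%.
- No Week 12 scan yet: 7/74 = 9.5% (9.4% with unrounded weeks).
- Per 10% of subjects whose stable disease would truly last 23 weeks, CBR falls by 0.257 × 10 = 2.6 points. Per 10% with qualifying stable disease, DCR falls by about 0.9 points.

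The first two percentages are upper bounds on misclassification: subjects who have already progressed, or whose response is already confirmed, are classified correctly. If there is no PK expansion and the MTD/RP2D is determined later than four weeks after the last entry, the gap shrinks.

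**3. PK-expansion subjects** (assumption: all 6 enrol, and enrol last)

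At the overall trial rate the six span 6/N × 74 weeks for a Phase 1 total of N.
- N = 54: 8.2 weeks, follow-up 4 to 12.2 weeks; all 6 are under 23 weeks.
- N = 24: 18.5 weeks, follow-up 4 to 22.5 weeks; all 6 are under 23 weeks.
- N = 18: 24.7 weeks; 6 × 19/24.7 = 4.6 of 6.
- Slower accrual because age strata must be filled, say 40 weeks (assumption): 6 × 19/40 = 2.9 of 6.

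**4. Phase 2 CBR, if the primary-analysis cutoff governs it** (assumption: uniform accrual)
- Accrual: 3 years less 16 weeks, 156 − 16 = 140 weeks.
- Affected: 20 × 7/140 = 1.0 of 20 per cohort. At twice the pace, 20 × 7/70 = 2.0 of 20.

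**The case against.** **A later cutoff may be intended.** Protocol 9.7 states "All statistical analyses will be performed by the sponsor or designee after the study is completed and the database is locked and released", and Protocol 5.1 names a separate cutoff: "The definition for end of the study is the date of data cutoff for the final analysis or last subject/last visit". SAP 5.4.1.2 says best overall response is determined once all of a subject's data are known, and SAP 3.2.3 keeps Phase 1 extension scans on schedule.

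For Phase 1 this does not remove the problem. The time at which an analysis is run does not move its data cutoff, and the Phase 1 cutoff carries no qualifier. Neither document dates a later cutoff or assigns CBR or DCR to one. For Phase 2 the objection stands in large part. That cutoff is labelled for the primary study analysis only, so a reader might infer that Phase 2 CBR is biased. The documents show only that its governing cutoff is undefined.

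**Scoring as failure is inferred.** This is true: the SAP does not say so. But its proportion definitions and full-set denominators leave no other result.

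**The effect is small beside sampling error.** A Clopper-Pearson interval for 3/18 runs from 3.6% to 41.4%. Phase 1 activity is described as preliminary, and its summaries are made if appropriate. This limits the importance. It does not make the interval cover a bias that always has the same sign.

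**The RP2D effect can be overstated.** A reader might infer that a third to a half of that dose level (6/18 to 6/12) must fall in the CBR gap. That requires all six PK subjects to enrol, at the overall rate, with a Phase 1 total of 24 or more. The protocol allows none to six, and a total of 18 or slower accrual gives fewer.

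**Conclusion.** The point holds for Phase 1. Followed as written, the SAP biases Phase 1 CBR and DCR downward according to enrolment date. Under uniform accrual over 74 weeks, up to about 26% of subjects are exposed for CBR and about 9% for DCR. PK-expansion subjects are the most exposed: up to all six under the conditions shown, about three of six if they accrue over 40 weeks, and none if no expansion is enrolled. The accrual patterns are assumptions; the shortfalls of 19 and 3 weeks come directly from the documents.

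For Phase 2 CBR there is a possible effect of about 1 in 20 per cohort at the planned pace, conditional on a cutoff the documents do not assign to it.

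A reader might extend this to the trial's main conclusions. That is not supported: MTD/RP2D, Week 16 ORR, the futility and final rules, Phase 2 DCR and DOR are unaffected. Phase 1 ORR is defined at data cutoff, so its dependence on that date is part of its definition. The harm is to descriptive secondary rates, and a correction is worthwhile because it is cheap.

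**What to change.** Keep every cutoff as it is.

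- **SAP 5.4.2.1 (Phase 1).** Keep the all-subject CBR and DCR. Beside them, report CBR for subjects first dosed at least 25 weeks before cutoff (Week 24 scan plus its one-week window) and DCR for those first dosed at least 13 weeks before (Week 12 plus one). Select on first-dose date only, whatever the outcome. By dose level, give the number excluded and the number with ongoing stable disease below each threshold.
- **SAP 5.4.2.2 (Phase 2).** State which cutoff governs CBR. Reconcile the per-cohort wording in SAP Section 5 with SAP 5.4.1.2 and Protocol 9.7.1.6. Apply the 25-week restriction only if the primary-analysis cutoff is the one used.

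**Cost.** SAP wording and a few extra table rows, with no new scans. The restricted denominators are smaller: under the same assumptions (25 − 4)/74 = 28% fewer Phase 1 subjects for CBR and (13 − 4)/74 = 12% fewer for DCR. If the restriction is needed in Phase 2, 20 × 9/140 = 1.3 of 20 per cohort are excluded. Most PK-expansion subjects would drop out of the restricted CBR, so the all-subject rate must stay beside it.

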5.1 Study Endpoints

5.1.1 Primary Endpoints

5.1.1.1 Primary Endpoints for Phase 1

- MTD and RP2D of lenvatinib in combination with everolimus
- Safety and toxicity of lenvatinib in combination with everolimus

5.1.1.2 Primary Endpoint for Phase 2

- ORR, defined as the proportion of subjects who have the best overall response (BOR) of complete response (CR) or partial response (PR), at Week 16.

5.1.2 Secondary Endpoints

Secondary endpoints for Phase 1 and Phase 2 are listed below.

- ORR at the time of data cutoff
- DCR, defined as the proportion of subjects who have the BOR of CR or PR or stable disease (SD) (SD duration ≥ 7 weeks since the first dose of the study treatment)
- CBR, defined as the proportion of subjects who have the BOR of CR or PR or durable SD (SD duration ≥ 23 weeks since the first dose of the study treatment)
- DOR, defined as the time from the date of the first documented CR or PR to the date of the disease progression objectively documented or death (whichever occurs first)
- Plasma PK of lenvatinib and trough concentrations of everolimus when administered in combination
- Safety and toxicity of lenvatinib in combination with everolimus in Phase 2.

5.1.3 Exploratory Endpoints

- Assess candidate alterations in genes and/or proteins that may contribute to tumor development and predictive marker of response in archival tumor tissue
- Correlative blood and tumor biomarkers of treatment effects and outcomes

5.2 Study Subjects

5.2.1 Definitions of Analysis Sets

The following analysis sets will be defined:

- **Evaluable Analysis Set**, defined as all evaluable subjects, who have measurable disease present at baseline and at least 1 postbaseline efficacy assessment, unless they have discontinued prior to the first efficacy assessment due to progressive disease. Efficacy analyses in Phase 2 will primarily be based on the Evaluable Analysis Set.
- **Safety Analysis Set**, defined as all subjects who received at least 1 dose of study drug (lenvatinib or everolimus). This will be the analysis set for disposition, demographic and baseline characteristics, previous anticancer medications, prior and concomitant medications, procedures and radiotherapy, medical history, efficacy analysis in Phase 1 as well as all safety evaluations.
- **Pharmacokinetic (PK) Analysis Set**, defined as subjects in the Safety Analysis Set who had at least 1 measurable postdose plasma concentration with an adequately documented drug administration history.
- **Pharmacodynamic Analysis Set**, defined as all subjects in Safety Analysis Set who had evaluable pharmacodynamic data.

All analyses will be presented by planned dose level group in Phase 1 and separately for each study cohort in Phase 2, unless otherwise specified. A summary table and listing will also be provided to identify subjects in each analysis set.

5.2.2 Subject Disposition

Subject disposition will be summarized using the Safety Analysis Set.

The number of subjects who were screened, and the number and percentage of subjects who enrolled, treated, and discontinued study treatment at the time of data cutoff will be summarized. The subjects who discontinued study treatment will be tabulated according to the primary reason for discontinuation by dose level group and overall in Phase 1, and separately for each study cohort in Phase 2. The reasons for prematurely discontinuing either lenvatinib or everolimus will be provided in a listing.

The end of study status (e.g., alive, death, withdrew consent, or lost to follow-up) at the data cutoff will also be summarized using the data from the survival follow-up eCRF by dose level group and overall in Phase 1, and separately for each study cohort in Phase 2.

Additionally, all subjects who failed screening will be listed with the primary reason for failure. Subject listings with relevant disposition information will be provided.

5.2.3 Protocol Deviations

All important protocol deviations will be determined and agreed upon after review of individual subject data prior to database lock. This review will be undertaken by the Study Director, Study Statistician, Study Data Manager and Study Clinical Operations Manager, in collaboration.

Important protocol deviations will be summarized and listed by dose level group in Phase 1 and separately for each cohort in Phase 2.

5.2.4 Demographic and Other Baseline Characteristics

Demographic and baseline characteristics for the Safety Analysis Set will be summarized by dose level group and overall in Phase 1, and separately for each study cohort in Phase 2.

The following demographic and baseline characteristics will be summarized as appropriate:

- Age (years)
- Age group (2 to <6 years, 6 to <12 years, 12 to <16 years, 16 to <18 years, 18 to 21 years, if applicable)
- Gender
- Race

- Ethnicity
- Baseline Karnofsky/Lanksy performance status score
- Height (cm)
- Height Percentile
- Baseline weight (kg)
- Baseline body mass index (BMI) (kg/m²)
- Body Surface Area

Previous anticancer medication will be summarized by dose level group and overall in Phase 1, and separately for each study cohort in Phase 2 as follows:

- Number of previous therapy regimens
- Duration of most recent previous anticancer therapy (months)
- Best response for most recent previous anticancer therapy (CR, PR, SD, progressive disease (PD), not evaluable, not applicable, unknown)
- Time from end of most recent previous anticancer therapy to first dose of study drug (months)
- Previous anticancer therapy (administered as adjuvant, neoadjuvant, metastatic, locally advanced, maintenance and unknown)
- Previous anticancer therapy preferred term

Previous anthracycline therapy will be summarized by dose level in Phase 1 and by each cohort in Phase 2 as follows:

- Number of subjects with any previous anthracycline therapy
- Duration of most recent previous anthracycline therapy (months)
- Time from end of most recent previous anthracycline therapy to first dose of study drug
- Previous anthracycline therapy preferred term

Previous radiotherapy will be summarized by dose level in Phase 1 and by cohort in Phase 2 as follows:

- Subjects with any previous radiotherapy
- Radiotherapy site (lymph node [neck/thoracic/abdominal and pelvic/other], bone [skull/spine/thorax/pelvis/extremities], brain, visceral [colorectal mass, lung mass, liver mass, chest, abdomen/pelvis], skin [trunk, extremity, head and neck], musculoskeletal [soft tissue-trunk, extremity, head and neck], miscellaneous)
- Tumor lesion at the site progressed since most recent previous radiotherapy (yes, no, not evaluated)
- Time from most recent previous radiotherapy to the first dose.

- Duration of most recent previous radiotherapy

Disease history and characteristics at study entry will be summarized by dose level in Phase 1 and by cohort in Phase 2 as follows:

- Solid tumor diagnosis classification
- Time since first diagnosis of solid tumor to date of first dose (months)
- Time since metastatic diagnosis to date of the first dose (months)
- Age at diagnosis (in years)
- Target lesions [yes/no] and nontarget lesions [yes/no] based on the measurable disease criteria at study entry using RECIST 1.1. or RANO as appropriate.

Tumor-node-metastasis (TNM) staging, stage group of Ewing sarcoma/PNET and Rhabdomyosarcoma at diagnosis and WHO Grading of Glioma for subjects evaluated by RANO will be provided in listing only.

Previous anticancer therapies, anthracycline therapy, previous radiotherapies, and disease history and characteristics at study entry will also be listed for each subject.

A subject data listing of medical history will be provided, including system organ class; current medical condition; date of diagnosis, surgical procedure, or onset of symptoms; and end date/ongoing. Coding will be done using the Medical Dictionary for Regulatory Activities (MedDRA) version 21.1 or higher.

